#### ***Analysis of pre-treatment and post-treatment adverse events***

- All pre-treatment adverse events by primary SOC and PT sorted by the internationally agreed SOC order and decreasing incidence of PTs within each SOC;
- All pre-treatment adverse events leading to treatment discontinuation (if any) by primary SOC and PT, sorted by the internationally agreed SOC order and decreasing incidence of PTs within each SOC;

- All post-treatment adverse events by primary SOC and PT, sorted by the internationally agreed SOC order and decreasing incidence of PTs within each SOC;
- All post-treatment SAEs by primary SOC and PT, sorted by the internationally agreed SOC order and decreasing incidence of PTs within each SOC.

### ***Subgroup of patients with 2 consecutive LDL-C <25 mg/dL***

If applicable, similar summaries of TEAEs as those described above will be also provided on the safety subgroup population of patients with 2 consecutive results of calculated LDL-C <25 mg/dL (as defined in [Section 2.1.5.3](#)) . Only TEAE for which it will be confirmed or unclear that they occurred, worsened or became serious the day or after the first level of calculated LDL-C <25 mg/dL will be considered.

Analysis of AESI including neurocognitive and neurological events and cataract (see selections in [Section 2.1.4.1](#)) will also be provided on the safety subgroup population of patients with 2 consecutive results of calculated LDL-C <25 mg/dL (as defined in [Section 2.1.5.3](#)).

#### **2.4.5.2 Deaths**

The following summaries of deaths will be generated for the safety population.

- Number (%) of patients who died by study period (on-study, on-treatment, post-study) and reasons for death adjudicated by the CEC
- Deaths in non-randomized patients or randomized but not treated patients
- Treatment-emergent adverse events leading to death (death as an outcome on the adverse event case report form page as reported by the Investigator) by primary SOC , HLGT, HLT, and PT showing number (%) of patients sorted by internationally agreed SOC order, with HLGT, HLT, and PT presented in alphabetical order within each SOC .

#### **2.4.5.3 Analyses of laboratory variables**

##### ***Descriptive statistics over time***

The summary statistics (including number, mean, median, Q1, Q3 standard deviation, minimum, and maximum) of all laboratory variables (central laboratory values and changes from baseline) will be calculated for each visit or study assessment (baseline, each post-baseline time point, last on-treatment and worst on-treatment value) by treatment group during the treatment period.

For glucose, this summary will be also provided according to the diabetic status at baseline. Only fasting samples will be summarized.

In addition, for some parameters of interest, mean changes from baseline with the corresponding standard error could be plotted over time in each treatment group.

### ***Potentially clinically significant abnormalities***

The incidence of PCSAs (list provided in [Appendix A](#)) as well as ALT increase as defined as AESI and hemoglobin decrease from baseline  $\geq 15$  g/L at any time during the TEAE period will be summarized by biological function (specified in [Section 2.1.4.3](#)) and treatment group whatever the baseline level and/or according to the following baseline status categories:

- Normal/missing;
- Abnormal according to PCSA criterion or criteria.

For glucose, this summary will also be provided according to the diabetic status at baseline. Only fasting samples will be summarized.

For parameters for which no PCSA criteria are defined, similar table(s) using the normal range will be provided.

### ***Hepatitis C***

The number and percentage of patients with a post-baseline seroconversion for hepatitis C test will be provided by treatment group in post-baseline (including the TEAE and post TEAE periods). Post-baseline seroconversion is defined for patients with a negative baseline status who had either a “positive ribonucleic acid” (RNA) or a “confirmed positive antibody with negative RNA” post-baseline status as defined in the table below. Other situations require case by case evaluation and will be described individually if relevant.

The status as regards to hepatitis C virus (HCV) for a patient will be defined as follows for all evaluations (baseline and post-baseline).

**Table 2 - Definition of the patient status regarding hepatitis C virus**

	Hepatitis C Antibody test result				
	Negative		Positive		
Reflexive test a – hepatitis C RNA test	Not available or HCV RNA not detected	HCV RNA detected	HCV RNA not detected b	HCV RNA detected	Not available
Hepatitis C status - label	Negative	Positive RNA	Negative b	Positive RNA	Positive Ab – no RNA available

a Test performed at the same time or after the antibody test in the pre-treatment period (for baseline evaluation), or post-baseline, respectively

b For post-baseline evaluation, a second antibody test with a different type of assay is to be done at the same date or after the first antibody test. The result of this test will modify the final hepatitis C status of the patient in some cases (see details in the text below the table)

The baseline evaluation will be based on tests performed during the pre-treatment period.

In case of multiple hepatitis C tests available for the post-baseline evaluation, the positive status of the patient will be defined as follows:

- “Positive RNA” status if at least 1 post-baseline positive RNA is detected, regardless of status of the patient at the end of treatment.

- Else “Positive Ab – no RNA available” status if no post-baseline reflexive RNA test is available for at least 1 post-baseline positive antibody test.

If no antibody test is available or with “indeterminate” as result pre-treatment or post-baseline, respectively, the RNA test (if available) will be used alone to determine the status of the patient. If no RNA is available then the hepatitis C status of the patient will be missing.

The post-baseline status “confirmed positive antibody with negative RNA” will replace “Negative” status as defined above in the case where no RNA was detected post-baseline and the 2 antibody tests surrounding the same visit (from 2 different types of assay) are positive.

For a conservative approach, the post-baseline status “Positive Ab – no RNA available” will not be modified by the availability of a second antibody test from a different assay.

#### ***Possible drug-induced liver injury***

The liver function tests, namely AST, ALT, alkaline phosphatase, and total bilirubin, are used to assess possible drug-induced liver toxicity. The proportion of patients with PCSA values at any post-baseline visit by baseline status will be displayed by treatment group for each parameter.

A graph of distribution of peak values of ALT versus peak values of total bilirubin will also be presented. Note that the ALT and total bilirubin values are presented on a logarithmic scale. The graph will be divided into 4 quadrants with a vertical line corresponding to  $3 \times \text{ULN}$  for ALT and a horizontal line corresponding to  $2 \times \text{ULN}$  for total bilirubin.

Graph and listing of possible Hy’s law cases identified by treatment group (eg, patients with any elevated  $\text{ALT} > 3 \times \text{ULN}$ , and associated with an increase in bilirubin  $\geq 2 \times \text{ULN}$ ) with ALT, AST, alkaline phosphatase, total bilirubin, and, if available, direct and indirect bilirubin, will be provided.

#### ***2.4.5.4 Analyses of vital sign variables***

The summary statistics (including number, mean, median, Q1, Q3, standard deviation, minimum, and maximum) of all vital sign variables (values and changes from baseline) will be calculated for each visit or study assessment (baseline, each post-baseline time point, last on-treatment and worst on-treatment value) by treatment group during the treatment period. In addition, for some parameters of interest, mean changes from baseline with the corresponding standard error could be plotted over time in each treatment group.

Vital signs without position filled in will only be used for the PCSA analysis described below.

The incidence of PCSAs at any time during the TEAE period will be summarized by treatment group.

#### **2.4.6 Analysis of other endpoints**

All measurements, scheduled or unscheduled, fasting or not fasting, will be assigned to analysis windows defined in [Section 2.1.5](#).

##### **2.4.6.1 Analyses of hs-CRP**

hs-CRP parameter (values and percent change from baseline) will be summarized on the safety population by analysis visit using number of available data, mean, SD, median, Q1, Q3, minimum, and maximum for each treatment group during the treatment period. The time profile will be plotted by treatment group with the medians, Q1 and Q3. The incidence of PCSA at any time during the TEAE period will be summarized by treatment group using descriptive statistics.

hs-CRP values greater or equal to 10 mg/L will be excluded from analyses in a second approach, since these are suggestive of concurrent infections.

##### **2.4.6.2 Analyses of HbA1c**

HbA1c parameter (values and change from baseline) will be summarized on the safety population by analysis visit using number of available data, mean, SD, median, Q1, Q3, minimum, and maximum for each treatment during the treatment period. Summary will be also provided according to the diabetic status at baseline (see [Section 2.1.1](#)). The time profile will be plotted by treatment group with the means and the corresponding standard errors (SEs). The incidence of PCSA at any time during the TEAE period will be summarized by treatment group using descriptive statistics.

##### **2.4.6.3 Analyses of patients with LDL-C <25 mg/dL (<0.65 mmol/L)**

The number and percentage of patients with 2 consecutive LDL-C <25 mg/dL (respectively, LDL-C <15 mg/dL, ie, 0.39 mmol/L) will be provided by treatment group on the safety population. Kaplan-Meier curves will be provided for the time to the first LDL-C <25 mg/dL (respectively 15 mg/dL) for these patients. For this analysis, patients without post-baseline LDL-C result or with only 1 post-baseline LDL-C result will not be included.

#### **2.4.7 Analyses of quality of life/health economics variables**

The analysis of data from EQ-5D instrument will be performed on QOL population. Baseline is defined as the visit 1 (Week 0) evaluation. Analysis window for efficacy parameters will be used to assign time points (see [Section 2.5.4.2, Table 4](#)).

### ***Individual EQ-5D items***

Response for each one of the 5 EQ-5D items will be summarized by visit for each treatment group using tables which will contain frequency and proportion of the population reporting level 1 (no problems), level 2 (some problems), and level 3 (extreme problems) by item and treatment group.

### ***EQ-5D utility score***

The raw value and the absolute change from baseline of the utility score will be summarized using mean, median, Q1, Q3, SD, minimum, and maximum for each post-baseline visit. Cumulative distribution functions for the absolute change in utility score from baseline will be displayed by treatment groups, at Week 4, Week 12, Week 24, and Week 36.

The absolute change from baseline in utility score to Week 4, Week 12, Week 24, and Week 36 will be analyzed using a MMRM model with fixed categorical effects of treatment group, randomization strata as per the registration center, treatment-by-time point interaction, strata-by-time point interaction, as well as, the continuous fixed covariates of baseline value and baseline value-by-time point interaction.

## **2.5 DATA HANDLING CONVENTIONS**

### **2.5.1 General conventions**

The following formulas will be used for computation of parameters.

#### ***Time***

1 month = 30.4375 days,

1 year = 365.25 days.

#### ***Age***

Age (years) = (Date of ACS diagnosis – Date of birth) / 365.25.

Age will be rounded using SAS INT function. In case date of ACS diagnosis and date of birth have the same month and day, then Age = year of ACS diagnosis – Year of birth.

#### ***BMI***

BMI (kg/m^2) = weight (kg)/ height (m)/ height (m).

For reporting such as Patients Profiles, or Listing of validation, the value will be rounded with 2 significant digits. But for calculating the summary, it will not be rounded.

### ***Time from index ACS diagnosis to randomization***

Time from index ACS diagnosis to randomization (weeks) = (Date of randomization – Date of index ACS diagnosis) / 7.

### ***Time from revascularization procedure to randomization***

Time from revascularization procedure to randomization (weeks) = (Date of randomization – Date of revascularization procedure) / 7.

### ***Time from diagnosis***

Time from diagnosis (years) = (Date of informed consent – Date of diagnosis\*) / 365.25.

(\*): In case the month of diagnosis would be missing, it will be put equal to JANUARY if the year of diagnosis equals the year of informed consent; it will be put equal to JUNE otherwise. In case that the day of the date is missing, the day will be put equal to "1st".

### ***Calculated LDL-C using the Friedwald formula***

$$\text{calculated LDL-C(mg/dL)} = \text{TC} - \text{HDL-C} - \text{TGs}/5$$

If TG values exceed 400 mg/dL (4.52 mmol/L), then calculated LDL-C will be missing.

### ***Conversion to standard international unit***

Should not be rounded at the time of calculation for conversion to standard international unit.

### ***Date of last administration of study treatment***

The date of the last administration is equal to the last date of administration reported on the end-of treatment case report form page, or missing if the last administration date is unknown.

### ***Renal function formulas***

eGFR value will be derived using the Japanese equation:

$194 \times (\text{serum creatinine in mg/dL})^{-1.094} \times (\text{age in years})^{-0.287}$  (x 0.739 if female). Serum creatinine rounded off to two decimal places will be used.

### ***Lipid variables, laboratory safety variables, hs-CRP***

For data below the lower limit of quantification (LLOQ)/limit of linearity, half of the lower limit value (i.e; LLOQ/2) will be used for quantitative analyses. For data above the upper limit of quantification (ULOQ) / limit of linearity, the upper limit value (ie, ULOQ) will be used for quantitative analyses.

## **2.5.2 Data handling conventions for secondary efficacy variables**

See [Section 2.1.3](#).

## **2.5.3 Missing data**

For categorical variables, patients with missing data are not included in calculations of percentages unless otherwise specified. When relevant, the number of patients with missing data is presented.

### ***Handling of computation of treatment duration and compliance if IMP or NIMP first or end of treatment date is missing***

If the last or first administration date is missing, the exposure duration and compliance will be used theoretical date.

### ***Handling of medication missing/partial dates***

No imputation of medication start/end dates or times will be performed. If medication date or time is missing or partially missing and it cannot be determined whether it was taken prior or concomitantly, it will be considered a prior, concomitant, and post-treatment medication, unless otherwise specified.

### ***Handling of adverse events with missing or partial date/time of onset***

Missing or partial AE onset dates and times will be imputed so that if the partial AE onset date/time information does not indicate that the AE started prior to treatment or after the TEAE period, the AE will be classified as treatment-emergent. No imputation of AE end dates/times will be performed. These data imputations are for categorization purpose only and will not be used in listings. No imputation is planned for date/time of adverse event resolution.

### ***Handling of adverse events when date and time of first administration is missing***

The exposure duration should be kept as missing.

### ***Handling of missing assessment of relationship of adverse events to IMP***

If the assessment of the relationship to IMP is missing for an adverse event, the adverse event will be considered as related to the IMP in the tables of possibly related adverse events, but no imputation will be done at the data level

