8.6 STORAGE CONDITIONS AND SHELF LIFE

The hospital pharmacists, or heads of the study sites, are responsible for storing the IMP (Praluent®) in a secure and safe place in accordance with local regulations, labeling specifications, policies, and procedures.

Control of IMP storage conditions, especially control of temperature (e.g., refrigerated storage) and information on in-use stability and instructions for handling the Sanofi compound should be managed according to the rules provided by the Sponsor.

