##### ***Analysis of all treatment-emergent adverse events***

The following TEAE summaries will be generated for the safety population.

- Overview of TEAEs, summarizing number (%) of patients with any:
  - TEAE;
  - Treatment emergent serious adverse event (SAE);
  - TEAE leading to death;
  - TEAE leading to permanent treatment discontinuation.
- All TEAEs by primary SOC, HLTG, HLT, and PT, sorted by the SOC internationally agreed order. The other levels (HLTG, HLT, and PT) will be presented in alphabetical order;

- All TEAEs regardless of relationship and related to IMP by primary SOC, HLT, and PT, sorted by the internationally agreed SOC order. The other levels (HLGT, HLT, and PT) will be presented in alphabetical order;
- All TEAEs regardless of relationship and related to LMT-NIMP by primary SOC, HLT, and PT, sorted by the internationally agreed SOC order. The other levels (HLGT, HLT, and PT) will be presented in alphabetical order;
  - AE related to LMT-NIMP is defines all AEs checked “Related” in “Atorvastatin/Rosuvastatin?” or “Lipid Modifying Therapy?” on the adverse event case report form page.
- All TEAEs regardless of relationship and related to LMTs by primary SOC, HLT, and PT, sorted by the internationally agreed SOC order. The other levels (HLGT, HLT, PT) will be presented in alphabetical order;
  - AE related to LMTs is defines all AEs checked “Related” in “IMP/Praluent?”, or “Atorvastatin/Rosuvastatin?”, or “Lipid Modifying Therapy?” on the adverse event case report form page.
- All TEAEs by primary SOC and PT, sorted by the internationally agreed SOC order and by decreasing incidence of PTs within each SOC (in the alirocumab group). This sorting order will be applied to all other tables by SOC and PT of TEAEs, unless otherwise specified.
- The frequency of AEs by SOC/PT and selected AEs over time during TEAE period (number of patients experiencing AE and percentage by patient-months) will be provided by time intervals defined as:  $\leq 12$  weeks,  $>12$  to  $\leq 24$  weeks,  $>24$  weeks using the actuarial method. Only the first event will be counted. Those intervals will be calculated from the randomization.
- All TEAEs that occurred with HLT incidence  $\geq 2\%$  in any treatment group, by primary SOC, HLT, and PT, sorted by internationally agreed SOC order and by alphabetic order for the other levels (HLT and PT);
- All TEAEs by maximal intensity (ie, mild, moderate, or severe), presented by primary SOC and PT.

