#### ***Analysis of all treatment emergent serious adverse event(s)***

- All treatment-emergent SAEs by primary SOC, HLT, and PT, sorted by the internationally agreed SOC order. The other levels (HLGT, HLT, and PT) will be presented in alphabetical order;
- All treatment-emergent SAEs regardless of relationship and related to IMP, by primary SOC, HLT, and PT, sorted by the internationally agreed SOC order. The other levels (HLGT, HLT, and PT) will be presented in alphabetical order.
- All treatment-emergent SAEs regardless of relationship and related to LMT-NIMP, by primary SOC, HLT, and PT, sorted by the internationally agreed SOC order. The other levels (HLGT, HLT, and PT) will be presented in alphabetical order.

- All treatment-emergent SAEs regardless of relationship and related to LMTs, by primary SOC, HLGT, HLT, and PT, sorted by the internationally agreed SOC order. The other levels (HLGT, HLT, and PT) will be presented in alphabetical order.
- All treatment-emergent SAEs by primary SOC and PT.

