### ***Handling of missing assessment of relationship of adverse events to LMTs***

If the assessment of the relationship to LMTs is missing for an adverse event, the adverse event will be considered as related to the LMTs in the tables of possibly related adverse events, but no imputation will be done at the data level

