### ***Handling of missing assessment of relationship of adverse events to LMT-NIMP***

If the assessment of the relationship to LMT-NIMP is missing for an adverse event, the adverse event will be considered as related to the LMT-NIMP in the tables of possibly related adverse events, but no imputation will be done at the data level

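### The SAP counts a missing IMP-relationship answer as IMP-related with no condition that the patient received IMP, so blanks in never-injected SoC patients inflate the comparator column

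*SAP*

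**What the plan says.** SAP 2.5.3 gives the rule for the IMP relationship: "If the assessment of the relationship to IMP is missing for an adverse event, the adverse event will be considered as related to the IMP". It continues: "in the tables of possibly related adverse events, but no imputation will be done at the data level". Parallel rules follow for two composite relationships: "the adverse event will be considered as related to the LMTs in the tables of possibly related adverse events" and "the adverse event will be considered as related to the LMT-NIMP in the tables of possibly related adverse events".

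The tables that use the IMP rule are in SAP 2.4.5.1: "All TEAEs regardless of relationship and related to IMP by primary SOC, HLT, and PT" and "All treatment-emergent SAEs regardless of relationship and related to IMP, by primary SOC". SAP 2.4.5 presents safety results by treatment group. SAP 2.3.2 defines the safety population to include patients treated with either alirocumab or standard of care. It assigns patients as treated, and a patient whose IMP injection proportion is below 50% goes to the SoC group.

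The IMP is alirocumab alone. Protocol 8.1 describes no other product, and protocol 8.6 speaks of "storing the IMP (Praluent®) in a secure and safe place".

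The AE page, as SAP 2.4.5.1 describes it, has separate relationship items for IMP/Praluent, for atorvastatin/rosuvastatin and for lipid modifying therapy. An event is LMT-NIMP-related if either of the last two is checked as related, and LMTs-related if any of the three is.

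**The concern.** Counting a missing causality answer as related is a conservative convention when the patient was exposed to the product. It is not conservative when the patient was not. In a trial with injections in one arm only, an unconditional rule can place drug-related events in the arm that did not get the drug.

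The SAP restricts other IMP summaries: the titration summaries in 2.4.3.1 are for the alirocumab group, and protocol 11.4.1 limits IMP exposure and compliance to that arm. The relationship rule and its tables have no such limit. The rule would suit a placebo-controlled design in which both arms are injected. The SAP's binary-endpoint text still refers to an odds ratio against placebo, so the rule may have been carried over, but that is an inference.

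Safety is a secondary objective, and protocol 11.4.3 plans no inferential safety testing. These descriptive tables are therefore the between-arm comparison of drug-related events that a reader will see. No efficacy result is touched.

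**Working it through.** **Plan's own figures.** The documents give no figure for this rule. The only plan number needed is the denominator in protocol 11.1 and SAP 1.3: 150 / (1 − 0.25) = 200 randomised, or 100 per arm. Percentages below can be read as patients per planned arm. SAP 2.4.5.1 counts patients, not events.

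**Is there a path from a blank to the table?** A never-injected SoC patient is in the safety population (2.3.2), appears in the SoC column (2.4.5), and has an AE with the IMP item blank. SAP 2.5.3 then counts that AE as IMP-related in the TEAE table and, if it is serious, in the SAE table. No section stops this.

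**Inputs for size.** The rates come from the Japanese phase 3 study summarised in protocol section 4 and serve only as illustration.
- Any TEAE: 83.3% control, 90.9% alirocumab.
- IMP-related TEAE: 20.3% alirocumab.
- Any treatment-emergent SAE: 12.5% control.
- Blank rate: not in the documents, so assumed over the range 0% to 100%.
- SoC any-TEAE rate: 83.3%, with 70% and 50% as assumed alternatives.

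**A. Blanks in SoC only.** Let b be the share of SoC patients with a TEAE who have at least one blank IMP answer.

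SoC % shown as IMP-related = (SoC any-TEAE %) × b

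| b | TEAE 83.3% | TEAE 70% | TEAE 50% |
|---|---|---|---|
| 0% | 0 | 0 | 0 |
| 5% | 4.2 | 3.5 | 2.5 |
| 10% | 8.3 | 7.0 | 5.0 |
| 25% | 20.8 | 17.5 | 12.5 |
| 100% | 83.3 | 70.0 | 50.0 |

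SoC overtakes alirocumab (20.3%, no blanks there) when b exceeds 20.3/83.3 = 24%, 20.3/70 = 29% or 20.3/50 = 41%.

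For the SAE table, the same bound at b = 100% is 12.5% of SoC patients.

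**B. Sporadic blanks at the same rate in both arms.** Assume that a fraction m of AEs is blank and that each patient with a TEAE has k AEs. Then q = 1 − (1 − m)^k.

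SoC % = 83.3 × q; alirocumab % = 20.3 + (90.9 − 20.3) × q

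- m = 1%, k = 2: q = 0.0199; SoC 1.7%, alirocumab 21.7%.
- m = 2%, k = 3: q = 0.0588; SoC 4.9%, alirocumab 24.5%.
- m = 5%, k = 4: q = 0.1855; SoC 15.5%, alirocumab 33.4%.

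The order does not reverse. The difference, 20.3 − 12.7q, moves only from 20.3 to between 20.0 and 17.9 points.

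**C. With an exposure condition.** Never-injected patients contribute 0 through imputation, whatever the blank rate. The rule still applies to exposed patients after their first injection.

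**D. Composite tables.** Both arms take a statin by design, so the statin item applies in both. Take a SoC event with the statin item answered as not related and the IMP item blank. The SAP does not say whether the LMTs composite is then missing. If one blank component is enough, the event becomes LMTs-related. If all components must be blank, it does not. The LMT-NIMP composite has the same ambiguity when a patient takes no non-statin LMT and that item is blank.

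**The case against.** The strongest reply is that the damage depends on an e-CRF that nobody can see in these documents. They do not say whether the IMP/Praluent item is hidden, mandatory, pre-filled or has a not-applicable option for SoC patients. Protocol 10.4.2 asks the investigator for a causality opinion on AEs in both arms, and protocol 13.4 provides for queries that the investigator must answer. Blanks may therefore be few or none. Against that, 10.4.2 asks about study treatment rather than IMP, so a SoC investigator could satisfy it through the statin item. This leaves the frequency unknown. It does not remove the missing condition.

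A reader might infer that the IMP item is naturally empty in SoC and that SoC will therefore show far more IMP-related patients than alirocumab. The documents do not support that. It needs blanks in about a quarter to two fifths or more of SoC patients with a TEAE, in practice a systematically empty field, and none in alirocumab.

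A reader might also infer that all six relationship tables are distorted (three relationships, TEAE and SAE). Only the two IMP tables clearly are. The other four depend on the undefined meaning of missing for a composite.

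Two further points stand in part. The tables show all events beside related events, and the underlying data are not imputed, so a gross artefact would be visible and recoverable. That limits the harm but does not justify publishing impossible counts. Also, an IMP-related event in the SoC column is not always spurious, because 2.3.2 can place partly injected patients there.

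**Conclusion.** The point holds as a defect in a stated rule. Applied as written, SAP 2.5.3 reports any blank IMP answer in a never-injected SoC patient as an IMP-related event, in two tables shown by arm. Confidence in the gap is high; confidence in its size is low.

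The effect is nil if the e-CRF forces an explicit answer. It is 1.7% to 15.5% of SoC patients if 1% to 5% of AEs are blank in both arms with 2 to 4 AEs per patient, and then the order of the arms does not change. About 83% SoC against 20% alirocumab is an extreme bound, not a forecast. All these figures borrow rates from a 52-week phase 3 study in a different population. The four composite tables are exposed only under one reading of an undefined term.

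**What to change.** In SAP 2.5.3:

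1. Apply missing = related to IMP only to AEs with onset on or after the first injection, in patients with at least one IMP injection. In all other cases set the IMP relationship to not applicable.
2. Apply the same exposure condition to each component of the LMTs and LMT-NIMP composites. Impute a composite as related only when an applicable component is missing and none is checked as related.
3. Report the number of missing relationship assessments by arm and by item.

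Do not blank out the whole SoC column. The as-treated SoC group in 2.3.2 can contain patients with some injections, and their IMP-related events should be shown. The condition belongs to the patient's exposure, not to the column.

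The cost is a few sentences in the SAP and one programming condition. The protocol's safety section (11.4.3) contains no such rule, so no protocol amendment is needed, and no new data are required. The change should be in place before the safety tables are produced.
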